4. STATISTICAL METHODOLOGY

4.1 General Principles

All collected study data will be presented in listings. All derivations and statistical analyses will be performed using SAS® software Version 9.4. Prior and concomitant medications will be coded using World Health Organization (WHO) Drug Dictionary Enhanced September 1, 2020. Adverse events (AEs) and medical history will be coded using Medical Dictionary for Regulatory Activities (MedDRA) Version 23.1.

Unless stated otherwise, descriptive summaries for continuous variables will include n (number of subjects with non-missing results), mean, standard deviation (SD), median, minimum, and

maximum. For categorical variables, n and percent will be provided. Percentages will be calculated out of the number of subjects in the given population with a non-missing result.

Nominal outcome summaries, presented by collection day and/or by time point, will be based on scheduled assessments as planned in the protocol. Unscheduled assessments will be presented in listings and will not be included in the analyses except for determination of Baseline as described in Section 5.1 and for the derivation of pharmacokinetic parameters. All other visit and time point collections will be as recorded on the electronic case report forms (eCRFs).

The protocol specifies that dosing with study drug will be on Day 0 with study days based on this date. In the context of the SAP and associated tables, figures, and graphs, study days from this point on will be based off of the day of dosing with the day of dosing being Day 1 and the day prior to dosing being Day -1. i.e., there will no Day 0.

Unless otherwise stated, hypothesis testing will be two-sided with an alpha level of 0.05.

4.2 Randomization

Eligible subjects will be randomly assigned to treatment arms A, B, C, D, E, and F in a [REDACTED] allocation ratio. [REDACTED]

4.3 Sample Size Considerations

	CLR_17_17 Statistical Analysis Plan	
	Date: 30-Sep-2022	Page 14 of 28

Arm A: MM-II 1 mL IA joint injection
Arm B: MM-II 3 mL IA joint injection
Arm C: MM-II 6 mL IA joint injection
Arm D: Placebo 1 mL IA joint injection
Arm E: Placebo 3 mL IA joint injection
Arm F: Placebo 6 mL IA joint injection

4.4 Sample Size Reassessment

[REDACTED]

After review of the results, the sample size could be kept as originally planned or increased up to 75% to a maximum of 609 subjects with any additional subjects to be randomized using an allocation ratio of [REDACTED]. The blinded sample size reassessment was performed as planned. After reviewing the results, the decision was made not to increase the sample size due to operational reasons.

4.5 Analysis Sets

[REDACTED]

Safety endpoints will be analyzed using the Safety Analysis Set. [REDACTED]

4.5.1 All Randomized Set

The ARS will include all randomized subjects. Subjects will be analyzed based on their randomized treatment.

[REDACTED]

[REDACTED]

[REDACTED]

	CLR_17_17 Statistical Analysis Plan	
	Date: 30-Sep-2022	Page 15 of 28

Safety Analysis Set

The Safety Analysis Set will include all randomized subjects who received the single dose of IP. Analyses will be based on the actual treatment received.

4.6 Subject Disposition

The number of subjects screened and in each of the analysis sets will be summarized by treatment, site, and overall, where applicable.

The number and percentage of subjects who completed the study will be presented by treatment, site, and overall for the All Randomized Set. Frequency and percentage of subjects who withdrew or discontinued from the study, and the primary reason for withdrawal, will also be summarized by treatment and overall.

4.7 Subject Demographics and Baseline Characteristics

Demographic data and subject characteristics at Baseline will be summarized descriptively. These characteristics will include age, sex, reproduction status, contraception method used, ethnicity, race, weight (kg), height (cm), BMI, Rhuematoid Factor, Anti-CCP, Index Knee X-ray, Analgesic

	CLR_17_17 Statistical Analysis Plan	
	Date: 30-Sep-2022	Page 16 of 28

Washout, and all subgroups presented in Section 4.12 by strata. Medical history will be presented by MedDRA system organ class (SOC) and preferred term (PT). Exposure with IP will be summarized by index knee and location of injection.

4.8 Prior and Concomitant Medications

Prior and concomitant medications are classified as follows.

- A prior medication is any medication taken prior to the date of the first dose of study drug.
- A concomitant medication is any medication taken on or after the date of the first dose of study drug.

A medication may be classified as both prior and concomitant. When determining prior or concomitant status for a medication, in the event that the start or end dates of the medication are unknown or incomplete, the medication will be considered as prior and concomitant unless the non-missing date information, if any, is enough to conclude that the medication could not be prior or, separately, could not be concomitant. Incidence of prior and concomitant medication use, according to medications collected on the prior/concomitant medication eCRF page (i.e., excluding rescue medications from the rescue medication dispensing and accountability eCRFs), will be summarized by World Health Organization (WHO) Drug dictionary coded terms Anatomical Therapeutic Chemical (ATC) classification and preferred name (PN).

4.9.1 Sensitivity Analysis

Multiple sensitivity analyses will be performed for the change from Baseline in WOMAC A pain score. One will repeat the primary analysis using the PPAS. The primary analysis will also be repeated for the FAS, but pooling the three placebo groups such that treatment in the model has four levels (1 mL, 3 mL, and 6 mL MM-II and pooled placebo). Comparisons of MM-II will be made against pooled placebo for this analysis.

An additional sensitivity analysis will be performed on the change from Baseline in WOMAC A pain score that imputes missing data using multiple imputations (MI) methodology. For the multiple imputations, subjects on MM-II that discontinue due to lack of efficacy will be imputed according to results for subjects randomized to 3 mL placebo. All other missing data will be imputed according to the subject's randomized treatment.

The multiple imputation method will be applied to missing WOMAC A pain scores from Baseline through Week 12 only. The imputation procedure will first begin by generating 100 imputed datasets for subjects that did not discontinue due to lack of efficacy or that were randomized to placebo. The 100 imputed datasets for the WOMAC A pain scores will be generated separately for each randomized treatment with a fully conditional specification (FCS) model using the regression method. The model will include covariates Baseline BMI group ($<30 \text{ kg/m}^2$, $\geq 30 \text{ kg/m}^2$ and $<35 \text{ kg/m}^2$, $\geq 35 \text{ kg/m}^2$) and Baseline VAS group (≤ 74 , ≥ 75). Following these initial imputations, 100 copies of the non-missing WOMAC A pain scores for subjects on MM-II that discontinue due to lack of efficacy will be generated. One of these copies will be added to each of the 100 imputed datasets generated for the 3 mL placebo group. A single imputation will then be generated for each of these 100 combined sets of data using the same FCS model as above. This will result in 100 imputed datasets for all subjects.

Change from Baseline to Week 12 in WOMAC A pain score from each of the 100 imputed datasets will be analyzed separately using an ANCOVA model with effect treatment and covariates site, Baseline WOMAC A pain score, Baseline BMI group ($<30 \text{ kg/m}^2$, $\geq 30 \text{ kg/m}^2$ and $<35 \text{ kg/m}^2$, $\geq 35 \text{ kg/m}^2$), and Baseline VAS group (≤ 74 , ≥ 75). For each comparison of interest, estimates and their associated standard errors from the ANCOVA models will be combined to produce a single overall

	CLR_17_17 Statistical Analysis Plan	
	Date: 30-Sep-2022	Page 19 of 28

estimate and standard error. Associated two-sided 95% confidence intervals and p-values will then be generated as appropriate.

The SAS® MI procedure will be utilized for imputing data. The first imputation step as described above will be implemented as follows.

```
Proc MI NIMPUTE=100 SEED=1867004294 MINIMUM=. . 0 0 0 0 0
      MAXIMUM=. . 4 4 4 4 4;
by trt;
class bmi vas;
var bmi vas w0 w1 w2 w4 w8 w12;
fcs reg(w0) reg(w1) reg(w2) reg(w4) reg(w8) reg(w12);
run;
```

Where:

trt = Treatment (Arms A, B, C, D, E, F)
bmi = Baseline BMI group
vas = Baseline VAS group
w0 = Baseline WOMAC A pain score
w1 = Week 1 WOMAC A pain score
w2 = Week 2 WOMAC A pain score
w4 = Week 4 WOMAC A pain score
w8 = Week 8 WOMAC A pain score
w12 = Week 12 WOMAC A pain score

The imputation step for subjects randomized to MM-II that discontinued due to lack of efficacy will be as above except with SEED=454120304, NIMPUTE=1, and without “by trt” since imputation will be based on a single treatment group.

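### The multiple-imputation sensitivity analysis in SAP 4.9.1 does not carry out its own two rules, because MM-II subjects who stop for lack of efficacy at any time leave their arm's model and help fit the placebo one; the net effect is small

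*SAP*

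**What the plan says.** SAP 4.9.1 opens the imputation analysis with two rules. For LOE withdrawals: "subjects on MM-II that discontinue due to lack of efficacy will be imputed according to results for subjects randomized to 3 mL placebo". For the rest: "All other missing data will be imputed according to the subject's randomized treatment". Only scores from Baseline to Week 12 are imputed.

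It then gives a two-step procedure.

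- **Step 1** starts by "generating 100 imputed datasets for subjects that did not discontinue due to lack of efficacy or that were randomized to placebo". These datasets are "generated separately for each randomized treatment with a fully conditional specification (FCS) model using the regression method".
- **Step 2** deals with the subjects left out: "100 copies of the non-missing WOMAC A pain scores for subjects on MM-II that discontinue due to lack of efficacy will be generated". Then: "One of these copies will be added to each of the 100 imputed datasets generated for the 3 mL placebo group". The same model is run once on each combined set. The `by trt` line is dropped, and the reason given is "since imputation will be based on a single treatment group".

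Two other places bear on who is in the LOE group. Protocol 5.1.1 sets a 26-week follow-up, so a subject can stop for LOE after Week 12. SAP 5.1 maps early-termination assessments from Days 72 to 99 to Week 12 when no scheduled Week 12 result exists.

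**The concern.** The rules and the procedure do not describe the same analysis.

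Under the second rule, an MM-II subject who leaves for a reason other than LOE should be imputed from everyone randomized to that arm. Step 1 instead fits the Arm A, B and C models after removing subjects who did badly enough to stop for LOE. Placebo subjects who stop for LOE stay in their own models, so the two sides are treated differently.

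Under the first rule, MM-II LOE withdrawals should be imputed from 3 mL placebo. In step 2 their own observed scores, from all three doses together, also help to fit that model. The set called a single treatment group is Arm E plus subjects from Arms A, B and C.

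This is the only readable analysis of the primary endpoint that departs from missing at random; SAP 5.3 bases all other analyses on available data. Its value lies in testing one stated assumption about LOE withdrawals, so its procedure should apply that assumption and nothing else.

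**Working it through.** **1. The plan's own figures.** The Protocol synopsis (Statistical Methods) gives 72 evaluable per arm, SD 0.59, difference 0.28, 80% power and alpha 0.05 (two-sided, SAP 4.1).

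- n per arm = 2 × 0.59² × (1.960 + 0.842)² / 0.28² = 70, against 72 stated.
- Power at 72 per arm = 81.3%, against 80%.
- Standard error of a difference = 0.59 × √(2/72) = 0.098.

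These figures reproduce and are not in dispute. The standard error is the yardstick below.

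**2. Which rows fit which model.**

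| Subject | Stated source of imputation | Rows used in fitting, as written |
|---|---|---|
| MM-II, missing for a reason other than LOE | own randomized arm | own arm without anyone who ever stops for LOE |
| MM-II, stops for LOE | 3 mL placebo | Arm E plus LOE withdrawals from Arms A, B and C |
| Placebo, any reason | own randomized arm | own arm, LOE withdrawals included |

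Each FCS regression is taken to be fitted on rows where that visit's score is present. LOE withdrawals without a Week 12 score then affect only the equations for earlier visits. The Week 12 equations are changed directly by LOE withdrawals who do have a Week 12 score: those who stop later, and those given a mapped score under SAP 5.1.

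**3. Share of the step 2 set that is MM-II.** Assume about 75 per main arm (348 × 3/14 = 74.6). This borrows the 3:3:3:1:3:1 ratio, which the Protocol states only for a sample-size increase; the initial ratio is redacted. If a proportion r of each MM-II arm stops for LOE, the share is 3r/(1 + 3r):

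- r = 2%: 4.5 subjects, 5.7%
- r = 5%: 11.3 subjects, 13%
- r = 10%: 22.5 subjects, 23%

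**4. Effect on the estimate.** The documents give no withdrawal rates, so every rate here is assumed. Large-sample simulation: 120,000 per arm, SD 0.59, changes of 0.52 and 0.80, LOE stopping dependent on current pain, placebo LOE rates 1.5 times those shown, other dropout random. BMI and VAS groups and the 0–4 bounds were left out. Each cell gives the SAP's procedure, then its stated rules. Differences are MM-II minus placebo, so negative favours MM-II.

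| LOE before / after Week 12 / other missing | Imputed Week 12, other reasons | Imputed Week 12, LOE | Treatment difference | Net shift |
|---|---|---|---|---|
| 3% / 0% / 5% | 1.185, 1.187 | 2.006, 1.975 | −0.2744, −0.2753 | +0.0009 |
| 5% / 5% / 5% | 1.128, 1.180 | 2.029, 1.929 | −0.2702, −0.2728 | +0.0026 |
| 5% / 5% / 15% | 1.127, 1.187 | 2.022, 1.941 | −0.2759, −0.2718 | −0.0040 |
| 10% / 10% / 10% | 1.061, 1.164 | 1.958, 1.872 | −0.2662, −0.2659 | −0.0003 |
| 10% / 10% / 20% | 1.049, 1.163 | 1.948, 1.868 | −0.2832, −0.2723 | −0.0109 |

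Other-reason dropouts are imputed 0.002 to 0.11 too low, and LOE dropouts 0.03 to 0.10 too high. The net shift runs from −0.011 to +0.003.

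Other simulations, with different correlation and dropout assumptions, agree on both directions. The largest shift in LOE values was about 0.12, and the largest net shift was +0.014, which is 0.014/0.098 = 0.14 of a standard error.

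**5. Where the effect comes from.** In a further run with 5% LOE before Week 12, 5% after, and about 8% other missing, moving all LOE withdrawals shifted other-reason values by −0.015 and the difference by −0.0007. Moving only those who stopped before Week 12 gave −0.0025 and +0.0001. Across four scenarios in that run the net shift was at most 0.0031 under the first reading and at most 0.0003 under the second.

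**The case against.** The strongest reply is that nothing is hidden. SAP 4.9.1 sets out the row selection, the copying and the combined fit, so the analysis is reproducible. The LOE rows must be present in step 2, or their imputations could not use their own earlier scores. As imputation stops at Week 12, a programmer might sensibly assume that only subjects with a missing score are moved. The numerical effect is also about a tenth of a standard error at most scenarios' extremes.

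Much of this stands. The rows do belong in step 2; the fault is only that they also fit the regressions. The size is small. But the time limit is nowhere in the text, and describing the procedure does not reconcile it with the two rules stated just before it. With the narrow reading, most of the numerical effect goes, but both mismatches remain for earlier visits.

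A reader might go further and infer that a gap between this analysis and the primary result could be produced by these departures, or that they tilt the result towards MM-II. The documents do not support that. They give no withdrawal rates, and the two departures oppose each other, with a net sign that changes between scenarios. With no drug effect, the step 1 departure alone shifted imputed values by −0.010 to −0.029 each. At 9% to 17% other missing this is 0.010 × 0.09 = 0.001 to 0.029 × 0.17 = 0.005 points on an arm mean.

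**Conclusion.** The point holds as a mismatch within SAP 4.9.1, confined to one sensitivity analysis. The step 1 models for Arms A, B and C omit every MM-II subject who ever stops for LOE, and the step 2 model is not fitted on 3 mL placebo alone. No readable section corrects this.

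It is minor. Individual imputed values move by roughly 0.002 to 0.12 points, while the treatment difference moves by about 0.01 or less in most scenarios (largest 0.014), against a standard error of about 0.10 and a planned effect of 0.28. No conclusion is likely to change, and the primary MMRM does not use these imputations.

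The sizes rest on assumed LOE and other withdrawal rates, about 75 subjects per main arm, and LOE stopping that depends on pain. The effect of the SAP 5.1 mapping was not quantified: it leaves fewer Week 12 scores missing, but gives some LOE withdrawals an observed one. The mismatch itself rests on the text alone.

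**What to change.** In SAP 4.9.1:

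- **(a) The key change.** Define the LOE group as MM-II subjects who discontinue for lack of efficacy and have no Week 12 score after the SAP 5.1 mapping. This one clause removes most of the effect.
- **(b) For full agreement with the second rule.** Fit step 1 by arm on all observed Week 0 to 12 scores of everyone randomized to that arm, and keep the imputed values only for subjects outside the LOE group.
- **(c) For full agreement with the first rule.** Fit step 2 on Arm E rows only, keeping LOE rows present solely so that their imputations condition on their own history. One way is the PROC MI MNAR statement with MODELOBS set to Arm E. Replace the remark about a single treatment group accordingly.

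The cost is a few sentences and small changes to two PROC MI calls, with no new data or subjects. Under (a), a subject who stops for LOE after a Week 12 score has any earlier missed visit imputed from the randomized arm. The ANCOVA uses only the Baseline and Week 12 scores, so an imputed intermediate visit does not enter that subject's analysed change.

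### The PROC MI bound lists in SAP 4.9.1 hold seven entries for eight variables, leaving the Week 12 score without its 0-4 limit or the step unable to run

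*SAP*

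**What the plan says.** SAP 4.9.1 prespecifies the imputation down to its seeds. Four parts of the code bear on this point:

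- Lower limits: "MINIMUM=. . 0 0 0 0 0"
- Upper limits: "MAXIMUM=. . 4 4 4 4 4"
- Variables: "var bmi vas w0 w1 w2 w4 w8 w12"
- Imputation models (closing bracket left off here): "fcs reg(w0) reg(w1) reg(w2) reg(w4) reg(w8) reg(w12"

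The CLASS statement names `bmi` and `vas`. The key below the code gives "w12 = Week 12 WOMAC A pain score". The analysis of the imputed data is then described as follows: "Change from Baseline to Week 12 in WOMAC A pain score from each of the 100 imputed datasets will be analyzed separately", using ANCOVA.

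The second step covers MM-II subjects who discontinued for lack of efficacy. Its code "will be as above except with SEED=454120304, NIMPUTE=1, and without" the BY statement on treatment. The method text in the same section says: "A single imputation will then be generated for each of these 100 combined sets of data using the same FCS model as above".

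Protocol 7.1.2 scores every WOMAC item from 0 to 4, and the Protocol synopsis defines WOMAC A as the mean of five items on that scale. SAP 5.3 limits imputation to this one sensitivity analysis.

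**The concern.** The two dots fit the two class variables, and 0 and 4 are the ends of the WOMAC A scale, so the code appears meant to keep every imputed score on the scale. Five pairs of limits cannot cover six scores. By position the one missed is Week 12, the only post-baseline score in the outcome of this ANCOVA. No reason is given for treating it differently from the other five.

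If the code runs as printed, subjects with missing data can be given negative Week 12 pain scores. If it does not run, prespecified code has to be changed after the SAP is final. Because the second step reuses the code, it carries the same short lists.

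**Working it through.** **Count** (SAP 4.9.1)

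| Element | Entries |
|---|---|
| MINIMUM | 7 (2 dots, 5 zeros) |
| MAXIMUM | 7 (2 dots, 5 fours) |
| VAR | 8 (2 class variables, 6 scores) |
| FCS regression terms | 6 |

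Paired in order, `bmi` and `vas` take the dots; `w0`, `w1`, `w2`, `w4` and `w8` take 0 and 4; `w12` takes nothing.

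**Planning inputs** (Protocol synopsis, sample size). Baseline mean 2.0, SD 0.59, improvement 0.8 (MM-II) and 0.52 (placebo). The plan's percentages reproduce: 0.8/2.0 = 40% and 0.52/2.0 = 26%. Week 12 means are 2.0 − 0.8 = 1.20 and 2.0 − 0.52 = 1.48, a difference of 0.28.

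**Assumptions**, because the visible text gives no figures: Week 12 SD s from 0.59 to 0.90; dropout d from 5% to 20% in each arm; half of MM-II dropouts for lack of efficacy, and so imputed from 3 mL placebo.

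**Share of unlimited draws outside 0-4.** For a normal draw with mean m this is Φ(−m/s) + 1 − Φ((4 − m)/s).

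| s | MM-II, m = 1.20 | Placebo, m = 1.48 |
|---|---|---|
| 0.59 | 2.10% | 0.61% |
| 0.75 | 5.49% | 2.46% |
| 0.90 | 9.21% | 5.26% |

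Example at s = 0.59: −1.20/0.59 = −2.034, and Φ(−2.034) = 2.10%. The upper tail is negligible there.

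**Mean shift caused by the limit.** With a = −m/s and b = (4 − m)/s, the truncated mean exceeds the plain mean by δ = s[φ(a) − φ(b)]/[Φ(b) − Φ(a)].

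- s = 0.59: δ = 0.0304 (MM-II) and 0.0102 (placebo)
- s = 0.90: δ = 0.1595 (MM-II) and 0.0905 (placebo)

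These take R² = 0, meaning earlier visits explain none of the Week 12 variance. At R² = 0.5, averaging δ over the predicted means with residual SD s√(1 − R²), the values fall to 0.0175 and 0.0055 (s = 0.59) and to 0.1030 and 0.0559 (s = 0.90).

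**Shift in the treatment difference.** The MM-II arm mean moves by d × (0.5 δ_MM-II + 0.5 δ_placebo) and the placebo mean by d × δ_placebo. The difference therefore moves by 0.5 d (δ_MM-II − δ_placebo).

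- Smallest case (d = 5%, s = 0.59, R² = 0.5): 0.5 × 0.05 × (0.0175 − 0.0055) = 0.0003
- Largest case (d = 20%, s = 0.90, R² = 0): 0.5 × 0.20 × (0.1595 − 0.0905) = 0.0069, and 0.0069/0.28 = 2.5%
- Largest case with no MM-II dropout imputed from placebo: 0.20 × 0.0690 = 0.0138, and 0.0138/0.28 = 4.9%

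Lower scores are better, so leaving out the limit makes the MM-II benefit look slightly larger.

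**Simulation.** 100 replicates, 100 imputations, 72 per arm, visit correlation 0.6, the same random numbers with and without the Week 12 limit. The imputation used sequential regressions on BMI group, VAS group and earlier visits; the ANCOVA omitted site; results were pooled by Rubin's rules.

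| s | Dropout | Apparent gain in MM-II benefit without the limit | SE ratio, without/with |
|---|---|---|---|
| 0.59 | 5 / 10 / 20% | 0.0005 / 0.0007 / 0.0019 | 1.004 / 1.006 / 1.013 |
| 0.90 | 5 / 10 / 20% | 0.0013 / 0.0019 / 0.0050 | 1.011 / 1.018 / 1.035 |

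Monte Carlo standard errors of the shifts are 0.0002-0.0003 at SD 0.59 and 0.0005-0.0009 at SD 0.90. The order of magnitude agrees with the closed form.

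**The case against.** The other side accepts the count and disputes its importance.

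*The consequence depends on how SAS reads a short list, which the documents do not say.* True. The point therefore claims neither branch. Under both, the printed code fails to apply 0-4 to all six scores.

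*If the step stops, it is noticed and repaired, and no result is affected.* This stands: every figure above belongs to the branch that runs. What remains is a change to prespecified code after finalization.

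*If it runs, no bias is shown.* This also stands. Limited and unlimited normal draws are both approximations to a bounded score, and the method text of SAP 4.9.1 mentions no limits. The correction makes the code consistent with its evident intent; it is not shown to be more accurate.

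*The 2.5% figure is not a ceiling.* Correct. It holds only for an SD up to 0.90, dropout up to 20% and half of MM-II dropout being for lack of efficacy. With SD 1.0, 20% missing and no imputation from placebo, the shift is 0.20 × (0.2111 − 0.1263) = 0.017, or 6.1% of 0.28.

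*The simulation departs from the plan, and its MM-II out-of-range share at SD 0.90 (7.6-7.9%) is below the normal figure of 9.2%.* It does simplify the plan: sequential regressions instead of full FCS, and no site term. The lower share is expected, because half of the MM-II dropouts are drawn from placebo: (9.21% + 5.26%)/2 = 7.2%. Drawing the regression parameters from 72 subjects adds some spread. The conclusion does not need the simulation.

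Loss of a list entry during text extraction cannot be fully excluded. It is unlikely, since two separate lists are each short by exactly one and the surrounding code is intact.

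**Conclusion.** The point holds as a minor coding error. That the lists are one entry short is certain from the printed code; what SAS then does is not established.

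If the step runs without the Week 12 limit, the treatment difference in this analysis changes by 0.0003 to 0.0069 points under the stated assumptions, by 0.0138 if no MM-II dropout is imputed from placebo, and by 0.017 if the SD is also raised to 1.0. All are small against 0.28. No effect on the trial's conclusion is claimed. The primary MMRM, the PPAS and pooled-placebo sensitivity analyses, alpha and sample size do not use this code.

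**What to change.** Add one entry to each list:

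`MINIMUM=. . 0 0 0 0 0 0`

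`MAXIMUM=. . 4 4 4 4 4 4`

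The second step inherits the change. As an optional clarification, add `by _Imputation_` to the description of the second-step code. The method text already requires one imputation for each of the 100 combined sets, so this only completes the code description.

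The cost is two characters and one optional line, with no new data. The downside is that limited draws raise the imputed Week 12 values, on average by 0.018 to 0.160 points when drawn from an MM-II arm and by 0.006 to 0.091 when drawn from placebo (SD 0.59 to 0.90, R² 0 to 0.5). The SAP already accepts this for the other five scores. If the sponsor wants Week 12 left unlimited, the SAP should say so and give the reason.
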